4.3 Research Questions

1. Primary question: Will a 6-session reconsolidation blockade treatment be efficacious in reducing core PTSD symptoms frequency and severity.
2. Secondary question: Are there psycho-social, cognitive, and biological markers (genetic, circulating, and neural) that can predict treatment response to reconsolidation blockade treatment?

5. Project Design

	Screen	T1 Baseline Week 0	T2 Pre-treatment (after 4-week waitlist)	Intervention Weeks 1–6	T3 Post-treatment Week 7 or 8	T4 Follow up 1 1-month	T5 Follow up 2 3-month
Research Activity	30-min phone call	4-hour clinical assessment: Medical ax* Psycho-diagnostic ax Heart rate variability Substances screen Self-report measures - PDI - PDEQ - PCL-5 - IES-R - BDI-I - PTGI	4-hour clinical assessment: MRI CANTAB Biological ax Hair Clip Self-report measures -PCL-5 -IES-R -BDI-I - Any sig. changes from T1?	50-min RT session in week 1 Thereafter once weekly 25-minute RT sessions in weeks 2-6 Saliva IES-R	4-hour clinical assessment: MRI CANTAB Psych interview Biological ax Self-report measures - PCL-5 - IES-R - BDI-I - WHOQOL - PSQI	50-min clinical interview Self-report measures -PCL-5 -IES-R -BDI-I	4-hour clinical assessment: MRI CANTAB Psych interview Biological ax Hair clip Heart rate variability Substances screen Self-report measures -PCL-5 -IES-R -BDI-I -PTGI

		- ITQ - CTQ - WHOQOL - PSQI Eligibility met/not met					-WHOQOL - PSQI
Setting	Tele-health	UniSC	UniSC	UniSC	UniSC	Telehealth	UniSC
Participants	>18yro Diagnosed PTSD	>18yro Diagnosed PTSD	>18yro Diagnosed PTSD	>18yro Diagnosed PTSD	>18yro Diagnosed PTSD	>18yro Diagnosed PTSD	>18yro Diagnosed PTSD
Identifiability during data collection	Identifiable	Identifiable	Identifiable	Identifiable	Identifiable	Identifiable	Identifiable
Identifiability during data storage	Re-identifiable	Re-identifiable	Re-identifiable	Re-identifiable	Re-identifiable	Re-identifiable	Re-identifiable
Identifiability at the time of publications	Non-identifiable	Non-identifiable	Non-identifiable	Non-identifiable	Non-identifiable	Non-identifiable	Non-identifiable
Recruiting methods	-Social media -Flyers -Website -Email circulated to referral networks	n/a	n/a	n/a	n/a	n/a	Email/phone call to previous participants who consented to future contact
Consent	Verbal via survey question	Written Unspecified Written consent requested to contact for future projects	Verbal	Verbal	Verbal	Verbal	Verbal
Risks and Benefits	-Distress -Discomfort	-Distress -Discomfort	-Distress -Discomfort -Side effects re: blood draw and imaging session	-Distress -Discomfort -Reduced PTSD symptoms -Adverse effects from study medication	-Distress -Discomfort -Reduced PTSD symptoms -Side effects re: blood draw and imaging session	-Distress -Discomfort -Reduced PTSD symptoms	-Distress -Discomfort -Reduced PTSD symptoms -Side effects re: blood draw and imaging session
Data Storage	Downloaded from Qualtrics, stored on R drive	R drive Consent forms – locked filing cabinets	R drive Consent forms – locked filing cabinets	R drive Consent forms – locked filing cabinets	R drive Consent forms – locked filing cabinets	R drive Consent forms – locked filing cabinets	R drive Consent forms – locked filing cabinets
Results/ Outcomes/ Future	Publication Future related projects	Publication Future related projects	Publication Future related projects	Publication Future related projects	Publication Future related projects	Publication Future related projects	Publication Future related projects

*ax = assessment

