4.2 Aims

Primary aim: To determine if a 6-session course of reconsolidation blockade (i.e., oral propranolol treatment combined with script-driven trauma recall) is efficacious in reducing PTSD symptom frequency and severity in adults.

Exploratory aims: To examine the psychosocial, neurocognitive, neurobiological, neuroimaging and physiological effects of reconsolidation blockade treatment in adult participants with PTSD.

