5.1 Methodological Approach

In this study, participants will receive manualised (Brunet & Lonergan, 2010) propranolol-based reconsolidation blockade treatment (hereafter called RT) once per week for six weeks in a single treatment arm. Each RT session will be conducted by trained practitioners. Session 1 will last 50 minutes while Sessions 2-6 will last 25 minutes and involve a script recall exercise to activate the specific trauma memory targeted for that session. Participants will be instructed to take the study oral medication (1mg/kg according to ideal weight) 60 minutes with a light snack before each scheduled RT session (i.e., 6 once-a-week doses over 6 weeks). The first dose will be taken on site under supervision of a registered nurse with access to a medical doctor. Subsequent doses will be taken at home before each treatment session. On the day of the first propranolol administration, the research trials

physician (GP) will be on-site to monitor for potential hypotensive events and ensure participant safety. This protocol builds on previous propranolol research and aligns with memory reconsolidation theory principles.

Throughout the study, participants will remain under the care of their existing treating team (i.e. medical practitioner, psychiatrist and/or psychologist), who will oversee any modifications to their existing treatments. RT will be used as an adjunctive treatment, allowing participants to maintain their current psychotropic medications, if any, under their physician's guidance. Any changes in medication will be documented by the study staff. It will be strongly recommended to participants and their treating team to not commence any new mental health treatments during the clinical study.

The primary outcome of the study is a change in PTSD symptomatology, assessed using the battery of psychological assessments (i.e., PCL-5, structured clinical interview) at several time points:

- T1 Baseline assessment (week 0)
- T3 post-treatment assessment (week 7 or 8)
- T5 Follow-up 2 (3 month)

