Please note: Once all the data pertaining to eligibility has been finalised (including a diagnosis of PTSD as assessed by the battery of tests in the psychological assessment protocol), and the results of the assessments having been reviewed and approved by the study team, the 'Eligibility Checklist' is completed, and the participant can be enrolled on the waitlist. Participants will then be given an ID Card stating their unique study ID, name of study, study drug, and study site. Participants will be instructed to keep this ID card on their person at all times, so that in the event of emergency (e.g. hospital admission) their treating staff will be aware of their participation in a drug study.

Pre-treatment assessment (T2) and waitlist

After the baseline assessment is completed, participants will be placed on a 4-week waitlist, during which time additional assessments will be completed:

Biological assessment

Biological assessment will be conducted by a study nurse and consist of a basic physical examination and blood sample collection consisting of:

- Height and weight measurement
- General observations; Blood pressure, pulse rate, pulse oximetry, respiratory rate and temperature measurement.
- Blood collection (~30 ml (2 tablespoons) - 2 x 10 ml K2EDTA tubes and 1 x 10 ml SST tube) by a certified phlebotomist in the pathology-certified room located within the National PTSD Research Centre
- Passive drool saliva collection
- Hair clip

Neuropsychological assessment

Cognitive functioning will be assessed using the Cambridge Neuropsychological Test Automated Battery (CANTAB) at pre-treatment (T2), post-treatment (T3) and follow-up 2 (T5). The CANTAB is a fully automated, self-administered neuropsychological test battery presented on an iPad. Once the participant details have been entered, the majority of instructions are delivered by CANTAB and the participant responds as instructed by the CANTAB. Specific cognitive tests were selected due to their known relationship to deficits in PTSD individual's cognition and functioning:

1. Motor Screening Task (MOT) – assess sensorimotor deficits and lack of comprehension,
2. Reaction Time (RTI) – assess reaction time, movement time and motor and mental response speeds,
3. Spatial Working Memory (SWM) – assess retention and manipulation visuospatial information,
4. Paired Associates Learning (PAL) – assess visual memory and new learning, and

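### WHOQOL-Bref and PSQI have a T1 baseline but no score after the 4-week wait, so their change to T3 and T5 mixes untreated and treated time

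*Protocol*

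**What the plan says.** The schedule table in section 5 (Project Design) sets the self-report measures by visit.

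- **T1 (baseline, week 0):** the list ends with "ITQ - CTQ - WHOQOL - PSQI Eligibility met/not met". Both scales are collected, at the visit that also settles eligibility.
- **T2:** headed "T2 Pre-treatment (after 4-week waitlist"). The entry is "Biological ax Hair Clip Self-report measures -PCL-5 -IES-R -BDI-I - Any sig. changes from T1". The last item asks whether anything has changed and yields no score on either scale.
- **T3:** "Self-report measures - PCL-5 - IES-R - BDI-I - WHOQOL - PSQI".
- **T5:** both scales again.

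The T2 text in section 5.4 says "After the baseline assessment is completed, participants will be placed on a 4-week waitlist, during which time additional assessments will be completed". It then describes the biological assessment, CANTAB and MRI. It mentions neither WHOQOL-Bref nor PSQI, nor the three questionnaires that the schedule places at T2.

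Section 5.1 describes a single treatment arm. Section 4.2 gives the relevant exploratory aim: "To examine the psychosocial, neurocognitive, neurobiological, neuroimaging and physiological effects of reconsolidation blockade treatment". Neither scale is named in the aims or the research questions.

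**The concern.** With no concurrent control, the wait is the only untreated comparison that the design contains. A T2 score lets the analyst start the contrast just before treatment and report the T1-T2 change separately. PCL-5, IES-R and BDI-I have that score, and CANTAB and MRI are first taken at T2. WHOQOL-Bref and PSQI are repeated after treatment but skipped at the one visit that would separate the two periods, and no reason is given.

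T1 is also the visit at which people seeking treatment are assessed for entry. Some improvement afterwards without treatment is plausible, through regression to the mean or because participants stay under their usual treating team. For these two scales any such improvement falls in the same interval as the treatment. A statement about the effect of treatment on quality of life or sleep would carry it, and it could not be removed once the participant has started treatment.

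**Working it through.** **Step 1. Which scales are scored when (schedule table, section 5).**

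| Scale | T1 | T2 | T3 | T5 |
|---|---|---|---|---|
| PCL-5, IES-R, BDI-I | yes | yes | yes | yes |
| WHOQOL-Bref, PSQI | yes | no | yes | yes |

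The section 5.4 text does not change this. For WHOQOL-Bref and PSQI the only available contrasts are T1-T3, T1-T5 and T3-T5. The first two span the wait, and the third contains no pre-treatment value.

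**Step 2. How much of T1-T3 is untreated.** Inputs: a wait of 4 weeks (sections 5 and 5.4), and "T3 post-treatment assessment (week 7 or 8") from section 5.1. The protocol does not say whether these weeks are counted from T1 or from the end of the wait. Counting from T1 does not fit: 4 weeks of waiting plus 6 weeks of treatment is 10 weeks, which is more than 8. I therefore count treatment weeks from the end of the wait.

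- T3 at week 7: 4 + 7 = 11 weeks, and 4/11 = 36% untreated.
- T3 at week 8: 4 + 8 = 12 weeks, and 4/12 = 33% untreated.

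**Step 3. What untreated drift could do (illustration only).** The protocol gives no effect size, SD, correlation or power for these scales, so there is no figure to reproduce. Assumptions: zero treatment effect; untreated improvement d of 0 to 0.3 SD of the raw score during the wait and none afterwards; T1-T3 correlation r of 0.6 or 0.8; n = 100, or 150 as the recruitment target in section 5.2; two-sided alpha 0.05 (section 5.10).

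The standardised mean change is dz = d / √(2(1 − r)). The rejection probability of the paired t-test comes from the noncentral t with n − 1 degrees of freedom and noncentrality dz·√n. For d = 0.1 and r = 0.6, dz = 0.1/√0.8 = 0.112, and at n = 100 the noncentrality is 1.12, giving 20%. For d = 0.1 and r = 0.8, dz = 0.1/√0.4 = 0.158, and at n = 150 the noncentrality is 1.94, giving 49%.

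| Assumed drift | n=100, r=0.6 | n=100, r=0.8 | n=150, r=0.6 | n=150, r=0.8 |
|---|---|---|---|---|
| 0 | 5% | 5% | 5% | 5% |
| 0.1 SD | 20% | 35% | 27% | 49% |
| 0.2 SD | 60% | 88% | 78% | 97% |
| 0.3 SD | 91% | 100% (rounded) | 98% | 100% (rounded) |

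If drift is expressed in SDs of the change score, a normal approximation at n = 150 gives 23%, 69% and 96% for 0.1, 0.2 and 0.3, and at n = 100 it gives 17%, 52% and 85%. The unit differs, but the pattern is the same.

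**The case against.** A reader might infer from the empty T2 cell that quality of life and sleep have no pre-treatment baseline. The documents do not support that. T1 precedes all treatment, is labelled baseline, and section 5.4 describes its questionnaires as a pre-treatment pack that includes both scales. What is missing is a second pre-treatment score, after the wait.

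A reader might also infer that the trial will count change during the wait as a treatment effect. No WHOQOL-Bref or PSQI contrast is stated, and section 5.10 leaves the variables to a later analysis plan. Only a limit on interpretation can be shown. That limit stands, because an analysis plan can choose among scores but cannot create one.

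Four further objections hold and limit the weight of the point.

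- By inference the two scales belong to the exploratory aims. For the secondary question, on predictors of response, a T1 value may be enough.
- A T2 score would not isolate the treatment effect. T2-T3 change still contains natural course, expectancy, usual care and any remaining regression to the mean. Using T1-T2 to correct it means assuming how a 4-week slope continues over 7 or 8 weeks.
- The rejection probabilities rest wholly on assumed drift. With none, the rate is 5%. With worsening, no false gain arises. Drift that continued during treatment would also inflate a T2-T3 test.
- Section 5.4 omits the T2 questionnaires but does not deny them, since its list need not be complete. This is an editorial mismatch and is not evidence about WHOQOL-Bref or PSQI.

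It can also be said that the wait matters more for the primary outcome: section 5.1 names T1, T3 and T5 and leaves out T2. PCL-5 is, however, collected at T2, so that can still be settled in the analysis. For these two scales it cannot.

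**Conclusion.** The point holds as a low-severity design gap. WHOQOL-Bref and PSQI have a valid T1 baseline but no score between the wait and the first dose. In a single-arm trial their T1-T3 and T1-T5 change therefore mixes untreated and treated time, and the two cannot be separated afterwards. For T1-T3 the untreated share is 4 of about 11 to 12 weeks, provided treatment weeks are counted from the end of the wait.

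The rejection rates of 20-49%, 60-97% and 91-100% at drifts of 0.1, 0.2 and 0.3 SD show how sensitive a T1-T3 test is to drift. They do not estimate the error rate of this trial, because drift and correlation are assumed. What justifies acting on an exploratory outcome is that the change is small and the loss is permanent for each participant once treatment starts.

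**What to change.** 1. Add WHOQOL-Bref and PSQI to the T2 self-report pack, completed at the end of the wait and before the first session.
2. Use T2 as the reference for T3 and T5 change on both scales, and report T1-T2 as the untreated change.
3. List the T2 questionnaires in the section 5.4 text so that it agrees with the schedule.
4. Reconcile the timing of T2. The schedule heading puts it after the wait, whereas section 5.4 has the assessments done in the course of it. This matters for PSQI, which asks about the past month: at the end of the wait that window covers almost exactly the untreated period, but earlier it reaches back before T1.

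The cost is 26 + 11 = 37 more items at T2, through the Qualtrics system already in use (section 5.9), at a visit that already takes place. The downside is a longer T2 pack. The report should still say that a T2 reference removes the wait from the contrast and does not stand in for a control arm.

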5.1 Methodological Approach

In this study, participants will receive manualised (Brunet & Lonergan, 2010) propranolol-based reconsolidation blockade treatment (hereafter called RT) once per week for six weeks in a single treatment arm. Each RT session will be conducted by trained practitioners. Session 1 will last 50 minutes while Sessions 2-6 will last 25 minutes and involve a script recall exercise to activate the specific trauma memory targeted for that session. Participants will be instructed to take the study oral medication (1mg/kg according to ideal weight) 60 minutes with a light snack before each scheduled RT session (i.e., 6 once-a-week doses over 6 weeks). The first dose will be taken on site under supervision of a registered nurse with access to a medical doctor. Subsequent doses will be taken at home before each treatment session. On the day of the first propranolol administration, the research trials

physician (GP) will be on-site to monitor for potential hypotensive events and ensure participant safety. This protocol builds on previous propranolol research and aligns with memory reconsolidation theory principles.

Throughout the study, participants will remain under the care of their existing treating team (i.e. medical practitioner, psychiatrist and/or psychologist), who will oversee any modifications to their existing treatments. RT will be used as an adjunctive treatment, allowing participants to maintain their current psychotropic medications, if any, under their physician's guidance. Any changes in medication will be documented by the study staff. It will be strongly recommended to participants and their treating team to not commence any new mental health treatments during the clinical study.

The primary outcome of the study is a change in PTSD symptomatology, assessed using the battery of psychological assessments (i.e., PCL-5, structured clinical interview) at several time points:

- T1 Baseline assessment (week 0)
- T3 post-treatment assessment (week 7 or 8)
- T5 Follow-up 2 (3 month)

5.2 Participants

Male and female adult participants aged 18 years and older, with a current diagnosis of non-complex PTSD, as assessed using the battery of tests within our psychological assessment protocol. The study will aim to recruit 150 participants. Investigators will keep a record of participants who were considered for the study but were not enrolled. This is done primarily to document the selection process, ensure transparency, and identify any potential selection biases. Please refer to section 5.3 for the process involved with the Participation Screening and Identification Log. Participants with a condition that may contraindicate the use of MRI will still be eligible to take part in the overall study. Only participants who meet all of the inclusion criteria and none of the exclusion criteria will be eligible to participate in the study.

Inclusion criteria:

- Persons aged 18 years +
- Participants must be able to understand Research Project Information Sheet (RPIS) and provide written informed consent on the Participant Informed Consent Form (PICF) (including both adequate intellectual capacity and fluency in English language)
- Diagnosis of PTSD
- Participants must undertake psychological, cognitive, and biological assessments, tolerate propranolol and not be taking any drugs that could contraindicate propranolol.
- Participants must have a current treating team who is managing their mental health diagnosis
- Persons of child-bearing potential must agree to use a *highly effective method of contraception

*Highly effective methods of contraception are listed below:

- o Hormonal methods of contraception including oral contraceptives containing combined estrogen and progesterone, a vaginal ring, injectable and implantable hormonal contraceptives, intrauterine hormone-releasing system (e.g. Mirena) and progestogen-only hormonal contraception associated with inhibition of ovulation o Nonhormonal intrauterine device (IUD)
- o Bilateral tubal occlusion
- o Vasectomised participant/partner with documented azoospermia 90 days after procedure, if that partner is the sole sexual partner.
- o Abstinence from heterosexual intercourse: when this is in line with the preferred and usual lifestyle of the participant.

Periodic abstinence (e.g., calendar, ovulation, post-ovulation methods) and withdrawal are not acceptable methods of contraception. Persons in the following categories are not considered persons of childbearing potential

- Person without a uterus
- Premenarchal

- Premenopausal with permanent infertility due to 1 of the following:
 - o Documented hysterectomy
 - o Documented bilateral salpingectomy
 - o Documented bilateral oophorectomy
- Postmenopausal - A postmenopausal state is defined as no menses for 12 months without an alternative medical cause

Exclusion criteria:

- Complex PTSD
- Significant psychiatric condition: psychosis, bipolar disorder, personality disorder, substance use disorder
- Any contraindication to propranolol as determined by the study physician
- Development of serious, adverse, or unexpected events/reactions during the trial
- Previous allergy or reaction to propranolol, or other beta-adrenergic blocking agent
- Participation in any other clinical study at the time of enrolment, or having received any investigation product within 30 days of the day of enrolment onto the study
- Currently pregnant, breastfeeding or intending to become pregnant during the course of the study.
 - o
- Any other condition that, in the opinion of the investigator, may adversely impact the safety of the participant or the accuracy of the study data

5.3 Recruitment and Consent

The study is scheduled to begin in November 2024, with the inclusion of the first ‘pilot’ participant. Data collection and analysis will continue throughout the study and the study endpoint is December 2027. Participants in the pilot will be recruited from contacts in our Realtime Database who have already expressed interest in participating in trauma-related clinical trials. Additional advertising for the research project will be undertaken by the TI/NPRC engagement and marketing team and will include direct emails sent to our established community partnerships. Recruitment will also occur online using approved advertisements and flyers on the TI/NPRC website and social media platforms such as Facebook. Additionally, participants may be recruited through public information sessions and forums organised by the TI/NPRC, both on and off-site, as well as through the Primary Health Network. Local healthcare professionals, such as general practitioners, specialists, medical officers, psychiatrists, and psychologists, will be informed about the study to facilitate referrals.

See Appendix C for a visual journey of the pathway through the program. Each participant is required to have a general practitioner (GP) or specialist referral prior to being included in this study who will continue to manage the participants’ mental health during the trial period. We will send the referring GP or specialist a letter detailing the participants' participation and outcomes of the trial upon completion of the study. If potential participants are referred by practitioners other than a GP or psychiatrist, we will ask them to obtain an appropriate referral from a GP or psychiatrist before including them in the study.

Every participant who is identified as potentially suitable for enrolment into the study will be entered into a Participant Screening and Identification Log. Information on the log will include the participant’s initials, participant’s date of birth, screening number, screening outcome (with a reason if found to be ineligible) and whether they are eligible to be rescreened with the approximate rescreen date recorded.

All potential participants will receive a digital version of the Research Project Information Statement (RPIS) via email prior to screening and the RPIS and consent form (Appendix A and B) via email prior to baseline (T1). The RPIS will detail the study process, including the assessment, intervention sessions, and data collection timeline.

Participants will be informed that their participation in the study is entirely voluntary. Only after reviewing the RPIS will participants have the option to provide their written consent. Participants will be encouraged to involve their treating doctor, family members, carers, and/or a support person when deciding whether they would like to participate or not. A support person can be present with participants during the research study to provide assistance and comfort as needed. If participants choose not to participate, they will be offered alternative

community service options. Participants will provide verbal consent before the following time points (screening, T2, treatment appointments, T3, T4, T5).

We will be seeking unspecified consent for the collection and future use of their data. This approach allows for the responsible and ethical use of collected information beyond the scope of the current research, supporting future studies in the field of mental health. Given the broad and evolving nature of mental health research, it is essential to have access to high-quality, ethically obtained data that can be used to answer new research questions as they arise. By consenting to unspecified future use, participants contribute to a legacy of mental health knowledge, aiding in the development of more comprehensive treatment approaches and contributing to the overall understanding of mental health conditions. Please refer to the informed consent operating procedure (Appendix N) for more detail on the consent process. All potential participants will be informed on their ability to withdraw from the study at any time.

We will incorporate an optional consent process for specific elements, including leftover biospecimens, video recordings, and contact details for future follow up. We will be seeking unspecified consent to use leftover biospecimens for future research, clearly explaining that future research will be in the mental health-related research space to gain a better understanding of the biology unpinning trauma and recovery. Any future studies would need HREC approval before being started and any analysis and distribution of results would be from deidentified and anonymised biospecimens in aggregate (so confidentiality is always maintained). By making this consent optional, participants can make informed choices about their comfort levels with contributing these specific types of data.

